In analyses of primary and secondary endpoint events at 3 months post-randomisation and during complete follow-up, follow-up will start immediately after randomisation. Follow-up will range from 1 year for the last recruited patients to about 7.5 years for first recruited patients. If the event numbers are sufficient, hazard ratios with 95% confidence intervals will be estimated by using Cox proportional hazards regression models, with patients censored at the time of first event of each type, death, last contact date, or the end of follow-up. The proportional hazards assumption for the treatment will be tested using Schoenfeld residuals. Kaplan-Meier survival analysis will be used to construct time-to-event curves, and the log-rank test will be used to evaluate whether there is a statistical significance difference in the cumulative risk of stroke between the two treatment groups.

We will also analyse short term outcomes to assess the operative risk. For this we have chosen a 30 day follow-up period but this may be adjusted before unblinding to results and analysis if we find stenting has not been carried out by 30 days in a significant number of individuals. For 30-days events, follow-up for each patient will start immediately after recruitment for patients allocated medical treatment alone and immediately after the stenting procedure for patients allocated stenting. If stenting was not performed in a patient allocated stenting, follow-up will begin directly after randomisation. The proportions of outcome events within 30-days of treatment will be compared with exact logistic regression to estimate odds ratios and 95% confidence intervals.

In additional analyses, provided that the event numbers are sufficient, we will adjust for centre and predefined risk factors (i.e., age, sex, body mass index and the vascular factors presented in Table 1). Hypothesis tests will be 2-sided using a significance level of 0.05. Statistical analysis will be performed using Stata (StataCorp, College Station, TX).

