#### 3.5. Sample size calculations

At trial initiation, we did power calculations using a power of 80% and two-sided significance level of 5%, and assuming that the risk of stroke in the medically treated arm would be 12% in year 1, 7% in years 2, and 5% in years 3 (i.e. 24% over a 3-year period). It was further assumed that the risk reduction in the stented arm would be 45% (including periprocedural rate). Based on these assumptions, the number of patients needed was estimated to be 490 (245 per arm). This number was increased by 10% to allow for stent failure, crossover, and loss to follow-up, thus giving a sample size of 540 patients. Because of early termination of the trial owing to low recruitment rate, the actual number of patients enrolled was 182.

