# Table 4. Serious adverse events within the first 30 days (intention-to-treat population)

CI, confidence interval; mRS, modified Rankin Scale; OR, odds ratio; TIA, transient ischemic attack.

ANALYSIS OF ANGIOGRAPHIC IMAGING DURING					
STENTING					
	Pre-Stenting	Immediate post-stenting			
Angiographic stenosis	? mean (SD)	? mean (SD)			
REPEAT NON-INVASIVE IMAGING AT 1 YEAR					
	At randomisation	At 1 year			
No. (%) with stenosis ≥50%					
Angioplasty/stenting					
Best medical therapy					
REPEAT NON-INVASIVE IMAGING AT 1 YEAR No. (%) with stenosis ≥50% Angioplasty/stenting Best medical therapy	At randomisation	At 1 year			

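### The 30-day operative-risk comparison gives an odds ratio and a P value but no interval for the absolute excess risk; a risk difference with a 95% CI should be added.

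*SAP*

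**What the plan says.** SAP Section 3.3 gives the purpose of the 30-day analysis: "We will also analyse short term outcomes to assess the operative risk". The method follows: "The proportions of outcome events within 30-days of treatment will be compared with exact logistic regression to estimate odds ratios and 95% confidence intervals". The same section adds: "Hypothesis tests will be 2-sided using a significance level of 0.05".

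Table 4, for the intention-to-treat population, has columns for number (%) in each arm, odds ratio with 95% CI, and P value. Its rows cover stroke, posterior circulation stroke with extracranial and intracranial lines, posterior circulation stroke or TIA, disabling stroke, major operation-related SAEs and death.

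Other parts of the SAP also bear on operative risk. Periprocedural stroke or death is a secondary endpoint with a hazard-ratio row in Table 3. Section 3.4 presents adverse events by arm. Neither place, nor Table 4, plans a risk difference or an interval for an absolute 30-day risk.

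Section 3.5 reports that "the actual number of patients enrolled was 182".

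**The concern.** The trial weighs an early procedural risk against a later benefit, so the practical 30-day question is how large the excess risk could be. An odds ratio answers this poorly when the comparator arm may have no events, because its upper limit is then infinite. The percentages in Table 4 show the observed difference but not its uncertainty.

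The P value does not fill the gap, because a sample of this size has low power for a moderate procedural excess. The trial could then report a non-significant result without stating any bound on the harm that the data leave open.

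**Working it through.** **Inputs.** The 182 patients are from SAP Section 3.5. An even split of 91 per arm is an assumption, based on the equal arms planned there (245 each). The two-sided 0.05 level is from Section 3.3. The medical-arm risk is from Section 3.5: "the risk of stroke in the medically treated arm would be 12% in year 1, 7% in years 2, and 5% in years 3", totalling 24%. The SAP gives no 30-day rate for stenting, so those rates below are assumptions.

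**The plan's own figure.** The only sample-size figure is for the primary endpoint. Reading the 45% reduction as a hazard ratio of 0.55, the three-year risks are 24% and 1 − 0.76^0.55 = 14.0%. At 80% power this needs 241 per arm, 482 in all, within 2% of the stated 490. There is no corresponding figure for the 30-day comparison.

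**30-day medical-arm risk.**
- Constant hazard within year 1: 1 − 0.88^(30/365) = 1.05%, or 91 × 0.0105 = 0.95 expected strokes.
- Falling hazard, Weibull form (an assumption): cumulative hazard 0.1278 × t^k with 0.1278 = −ln 0.88.
  - Fitted to 24% at three years: k = ln(0.2744/0.1278)/ln 3 = 0.695, giving 2.2% at 30 days.
  - Fitted to compounded yearly risks, survival 0.88 × 0.93 × 0.95 = 0.777: k = 0.617, giving 2.7%.

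**Chance of no medical-arm stroke, (1 − p)^n.**

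| 30-day risk | n = 91 | n = 45 | n = 30 |
|---|---|---|---|
| 1.05% | 38% | 62% | 73% |
| 2.2% | 13% | 36% | 51% |
| 2.7% | 8% | 29% | 44% |

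The 30 and 45 illustrate a location row; the SAP does not give those sizes. Posterior circulation stroke cannot be more frequent than any stroke, so these any-stroke risks, if anything, understate the chance of an empty cell in those rows.

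**Chance of missing a true excess.** All pairs of binomial outcomes at 91 per arm were enumerated, counting exact conditional two-sided P < 0.05 in the direction of harm.

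| Medical vs stenting (assumed) | Power | Missed |
|---|---|---|
| 1% vs 5% | 15.6% | 84% |
| 1% vs 6% | 26.2% | 74% |
| 2% vs 6% | 14.3% | 86% |
| 1% vs 8% | 50.0% | 50% |
| 1% vs 10% | 70.7% | 29% |

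With 0, 1 or 2 medical-arm events, significance needs at least 6, 8 or 10 stenting-arm events.

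**Same data on both scales (stenting vs medical).**
- 5/91 vs 0/91: the conditional maximum-likelihood odds ratio is infinite (median-unbiased 7.0), 95% CI 0.94 to infinity, P = 0.059. The risk difference is 5.5 percentage points, Newcombe 95% CI 0.4 to 12.2.
- 5/91 vs 1/91: odds ratio 5.2 (0.56 to 250). The risk difference is 4.4 points (−1.4 to 11.2).
- 0/91 vs 0/91: no odds ratio. The Newcombe limits are ± z²/(n + z²) = ± 3.84/94.84 = ± 4.1 points.

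**The case against.** Exact logistic regression is a sound choice for sparse events, and nothing in this part of the SAP is false or contradictory. The per-arm counts are tabulated, so a reader can compute a risk difference and its interval. When the medical arm has no events, the lower limit, a median-unbiased odds ratio and the counts remain, and 0.94 to infinity would hardly reassure anyone. These points stand; they make this an improvement, not the correction of an error.

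The low power is also mostly a matter of size, not method. For 80% power, 1% versus 6% needs 211 per arm (250 with continuity correction), within the 270 implied by the planned 540. For 1% versus 5% the figure is 285 (333), so even full enrolment would have fallen somewhat short. The risk difference recovers only part of the loss: requiring its Newcombe lower limit to exceed zero still misses 74%, 61% and 78% at 1% vs 5%, 1% vs 6% and 2% vs 6%.

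A reader might infer three stronger things that the SAP does not support:
- **That operative risk rests on the odds ratio alone.** Counts and percentages, the periprocedural endpoint and the adverse-event presentation are also planned.
- **That an unbounded ratio is the expected result.** For the main stroke row even the constant-hazard figure is 38%, and the SAP's yearly risks fall, which points to lower values.
- **That the SAP would treat P > 0.05 as proof of safety.** It states no such rule. The comparison with medical therapy in Section 1 concerns preventing recurrent stroke, not operative safety.

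**Conclusion.** The concern holds as a cheap improvement. The 30-day analysis plans no interval for the absolute excess risk, and its chosen effect measure can become unbounded or undefined under the SAP's own risk assumptions.

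For the main stroke row, the chance of an empty medical arm runs from about 8% to 38%, depending on how the first-year risk is spread; it is higher in the location rows. The miss rates depend on stenting rates that the SAP does not give and should be quoted only together with those rates. They show that a non-significant 30-day result would carry little information about safety. All figures assume 91 patients per arm.

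**What to change.** In Section 3.3 and Table 4, add for each 30-day stroke and death row the absolute risk difference, stenting minus medical, with a Newcombe or Miettinen-Nurminen 95% CI. Keep the exact odds ratio alongside it, marked as unbounded or not estimable where that applies.

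Add one sentence to Section 3.3 saying that operative risk is interpreted from the upper limit of the risk-difference interval, and that P > 0.05 is not evidence of no excess risk.

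The cost is one table column and a sentence, with no new data. The downside is that the limits will be visibly wide.

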#### 3.4. Adverse Events

Adverse events (AEs), including serious adverse events (SAEs), have been recorded as specified in the protocol (pages 10-12). AEs and SAEs will be defined as in the protocol and presented stratified by treatment group.

#### 3.5. Sample size calculations

At trial initiation, we did power calculations using a power of 80% and two-sided significance level of 5%, and assuming that the risk of stroke in the medically treated arm would be 12% in year 1, 7% in years 2, and 5% in years 3 (i.e. 24% over a 3-year period). It was further assumed that the risk reduction in the stented arm would be 45% (including periprocedural rate). Based on these assumptions, the number of patients needed was estimated to be 490 (245 per arm). This number was increased by 10% to allow for stent failure, crossover, and loss to follow-up, thus giving a sample size of 540 patients. Because of early termination of the trial owing to low recruitment rate, the actual number of patients enrolled was 182.

# 4. PROPOSED TABLES AND FIGURE LEGENDS

Table 1. Baseline characteristics of patients enrolled into the VIST, according to treatment group (intention-to-treat population) (per protocol data will be presented in columns to the right or in a separate similar table)

Characteristic a	Best medical treatment	Angioplasty/stenting	P value b
	group (n = xx)	group (n = xx)	
Age (years)			
Male, n (%)			
Body mass index c			
Vascular risk factors			
Treated hypertension			
Treated hyperlipidaemia			
Previous myocardial infarction			
Angina in last 6 months			
Peripheral artery disease			
Atrial fibrillation			
Qualifying event			
TIA			
Non-disabling stroke d			
Location of vertebral artery target			
stenosis			
Extracranial (V1 to V3)			
Intracranial (V4)			
Modified Rankin Score			

TIA, transient ischemic attack; VIST, Vertebral artery Ischaemia Stenting Trial.

a Values are number (%) of patients or mean (± SD).

b Treatment groups are compared using Fisher's exact test or *t* tests.

c BMI is calculated as weight (kg) divided by height (m) squared.

d Modified Rankin scale score  $\leq$ 3 at inclusion.

Table 2. Medica	l treatment and b	ood pressure	and risk factor	control over th	ne first 30 days over

# the whole study follow-up

	Best medical treatment group (n = xx)		Angioplasty/stenting group (n = xx)		
	First 30 days	Whole follow-up a	First 30 days	Whole follow-up a	
Antiplatelet medication					
Aspirin alone					
Clopidogrel alone					
Aspirin and clopidogrel					
Other					
Oral anticoagulants					
Statin therapy					
Antihypertensive medication					
Blood pressure b					
Systolic (mmHg)					
Diastolic (mmHg)					
Treated diabetes mellitus					
Non-insulin dependent					
Insulin dependent					
Current smoking					
a Where treatments ch	anged during follo	w-up the treatment give	n for the majority	of follow-up is	

recorded.

b Blood pressure measurements were only recorded at clinic follow-ups at 3 months and 1 year.

Table 3. Primary and secondary endpoint events during follow-upa (intention-to-treat population) (per-protocol data will be presented in columns to the right or in a separate similar table)

	No. (%) of patients/person-months			
	Best medical treatment	Angioplasty/stenting	HR (95% CI)	P value
	group (n = xx)	group (n = xx)		
Primary endpoint				
Fatal or non-fatal stroke in any arterial territory b				
Extracranial vertebral artery target stenosis				
Intracranial vertebral artery target stenosis				
Secondary endpoints				
Fatal or non-fatal stroke in any arterial territory b at 3 months				
Posterior circulation stroke b				
Periprocedural stroke or death				
Posterior circulation stroke or TIA				
Death from any cause				
CI, confidence interval; HR, hazard ratio; mRS, modified Rankin S	cale; TIA, transient ischemic	attack.		

a Complete follow-up (≥1 year) if not otherwise indicated.

b Including periprocedural (30 days post-procedure) stroke.

	No. (%) of			
	Best medical treatment	Angioplasty/stenting	OR (95% CI)	P value
	group (n = xx)	group (n = xx)		
Cerebrovascular event				
Fatal or non-fatal stroke				
Posterior circulation stroke				
Extracranial				
Intracranial				
Posterior circulation stroke or TIA				
Any disabling stroke (mRS score ≥3)				
Major operation related SAEs				
Death from any cause				

# Table 4. Serious adverse events within the first 30 days (intention-to-treat population)

CI, confidence interval; mRS, modified Rankin Scale; OR, odds ratio; TIA, transient ischemic attack.

ANALYSIS OF ANGIOGRAPHIC IMAGING DURING					
STENTING					
	Pre-Stenting	Immediate post-stenting			
Angiographic stenosis	? mean (SD)	? mean (SD)			
REPEAT NON-INVASIVE IMAGING AT 1 YEAR					
	At randomisation	At 1 year			
No. (%) with stenosis ≥50%					
Angioplasty/stenting					
Best medical therapy					
REPEAT NON-INVASIVE IMAGING AT 1 YEAR No. (%) with stenosis ≥50% Angioplasty/stenting Best medical therapy	At randomisation	At 1 year			

#### **FIGURE LEGENDS**

Figure 1. Flow of patients (see page 2)

Figure 2: Kaplan-Meier curves of cumulative probability of any stroke during follow-up, according to treatment group (intention-to-treat population)

Log-rank test is used to test the hypothesis that the cumulative incidence of stroke is the same in the two groups.
